## 5. TREATMENT PLAN

### 5.1. Screening and Biomarker Cohorts

Once subjects have been registered for the study, primary tissue (from RP or diagnostic core biopsies) will be obtained, including blocks and any slides. For non-BIDMC institutions, a BIDMC clinical research assistant should be contacted by email ([[contact]](mailto:[contact])) with the subject line including protocol number and “Tissue Collection.”

[name] will perform screening PD-L1 immunohistochemistry at BIDMC. “Positive” PD-L1 expression is defined for this study by  $\geq 1\%$  Combined Positive Score (CPS), which is the number of PD-L1-staining cells (tumor cells, lymphocytes, macrophages) divided by the total number of viable tumor cells, multiplied by 100. For any cases deemed positive, tissue will be sent to Acupath Laboratories, Inc., a CLIA-certified laboratory, for confirmation immunohistochemistry. For cases deemed negative, these will also be sent to Acupath for confirmation, but only so long as the PD-L1-negative cohort is open; once the target accrual of 14 patients in this cohort is reached, subsequent cases deemed to be PD-L1 negative by [name] will not be sent for Acupath confirmation and these subjects would not be eligible for the study.

Specifications for shipment of tissue to Acupath are:

- Slides must be 4-5 microns per section, unbaked, placed in a slide holder box so slide is on its side
- Slides must be accompanied by an information sheet (please see Appendix 2)

Ship via FedEx to:

[name]  
Acupath Labs  
[name]  
[name]  
[contact]

Office: [contact] [name]  
[contact]

As noted in this trial schema, this study involves two cohorts, a PD-L1-positive cohort and a PD-L1-negative cohort. Subjects will be assigned to one of these cohorts once results of immunohistochemistry (with confirmation from Acupath) are available. Until the PD-L1-negative cohort has accrued 13 subjects, study treatment may begin once the lead site has received archival tissue; PD-L1 status may be assigned retroactively. Once the 13th PD-L1-negative subject has been accrued, then all subjects will need to have PD-L1 status assigned before they may start study treatment. Once a cohort reaches maximum enrollment (20 subjects for the PD-L1-positive cohort; 14 subjects for the PD-L1-negative cohort), no further subjects may be enrolled to that cohort. It is likely that the PD-L1-negative cohort will close first. At this point, subjects may still be screened, but any deemed to be PD-L1-negative by [name] will be excluded from the trial without confirmation from Acupath.

After the PD-L1-negative cohort closes, a tissue pre-screening consent will occur. Potential participants will be consented to have their tissue evaluated for PD-L1 expression. If they are found to be PD-L1-negative, no further study-related activities will occur. If they are found to be PD-L1-positive, then full informed consent will occur and this will begin the study screening period.

After review and selection of tissue for PD-L1 testing, remaining tissue will be used for next-generation sequencing and exploratory studies.

In the event of limited quantity of tissue, priority order for tissue specimens is:

1. PD-L1 expression assessment
2. Next-generation sequencing
3. Exploratory studies

## **5.2. Nivolumab Administration**

Nivolumab will be given on day 1 of a 28-day cycle at a dose of 480 mg intravenously (IV). All visits have a window of +/- 3 days (see Study Calendar, section 7).

The administration of nivolumab infusion must be completed within 24 hours of preparation. If not used immediately, the infusion solution may be stored under refrigeration conditions (2°C to 8°C, 36°F to 46°F) for up to 24 hours, and a maximum of 8 hours of the total 24 hours can be at room temperature (20°C to 25°C, 68°F to 77°F) and room light. The maximum of 8 hours under room temperature and room light conditions includes the product administration period. The unopened vials can be stored at room temperature (up to 25°C, 77°F) and room light for up to 48 hours.

Nivolumab injection is to be administered as an IV infusion over 30 minutes (acceptable window is 25 minutes to 40 minutes) through a 0.2-micron to 1.2-micron pore size, low-protein binding (polyethersulfone membrane) in-line filter at the protocol-specified doses

and infusion times. It is not to be administered as an IV push or bolus injection. Nivolumab can be infused undiluted or diluted so as not to exceed a total infusion volume of 160 mL. For patients weighing less than 40 kilograms (kg), the total volume of infusion must not exceed 4 mL per kg of patient weight.

### **5.3. Concomitant Medications**

#### **5.3.1. Allowed Concomitant Medications**

All treatments that the investigator considers necessary for a subject's welfare may be administered at the discretion of the investigator in keeping with the community standards of medical care.

#### **5.3.2. Prohibited Concomitant Medications**

Concomitant systemic or local anti-cancer medications or treatments are prohibited in this study while receiving nivolumab treatments.

Patients may not use any of the following therapies during the study or for the 4 weeks preceding the PSA values used to determine subject eligibility:

- Any non-study anti-cancer agent (investigational or non-investigational), including but not limited to bicalutamide or other anti-androgens; GnRH analogs/antagonists; dutasteride, finasteride, or other 5 alpha-reductase inhibitors; or alternative medications known to alter PSA (e.g. phytoestrogens and saw palmetto)
- Any other investigational agents
- Immunosuppressive agents (except as needed to treat toxicities that develop on therapy)
- Physiologic replacement doses of corticosteroids are permitted if required
- Any non-oncology vaccine therapies used for the prevention of infectious diseases (for up to 30 days prior to or after any dose of study drug)

**NOTE:** Patients are permitted to receive the seasonal influenza vaccine. If seasonal influenza vaccine is considered, killed vaccines should be recommended. Patients are permitted to receive all COVID-19 vaccines.

## **6. TOXICITIES AND DOSE DELAYS**

Please see Section 10 for expected toxicities related to nivolumab therapy.

### **6.1. Management of Immune-Related Adverse Events**

Please see Appendix 1 for tables summarizing management of immune-related adverse events plus management algorithms for specific organ systems.

## 6.2. Dose Modifications

There will be no dose modifications permitted. Dose reductions or dose escalations are not permitted.

## 6.3. Dose Delay Criteria

Dose delay criteria apply for all drug-related adverse events.

Nivolumab administration should be delayed for the following:

- Any Grade  $\geq 2$  non-skin, drug-related adverse event, including grade 2 liver test elevation, with the following exceptions:
  - Grade 2 drug-related fatigue
- Any Grade 3 skin, drug-related adverse event
- Any Grade 3 drug-related laboratory abnormality
- Any new-onset moderate or severe neurologic signs or symptoms. For a diagnosis of immune-mediated encephalitis, permanently discontinue.
- Any adverse event, laboratory abnormality, or intercurrent illness which, in the judgment of the site investigator, warrants delaying the dose of study medication.

## 6.4. Criteria to Resume Treatment

Subjects may resume treatment with study drugs when the drug-related AE(s) resolve to Grade  $\leq 1$  or baseline value, with the following exceptions:

- Subjects may resume treatment in the presence of Grade 2 fatigue
- Subjects who have not experienced a Grade 3 drug-related skin AE may resume treatment in the presence of Grade 2 skin toxicity
- Drug-related pulmonary toxicity, diarrhea, or colitis, must have resolved to baseline before treatment is resumed
- Drug-related endocrinopathies adequately controlled with only physiologic hormone replacement may resume treatment

If the criteria to resume treatment are met, the subject should restart treatment at the next scheduled timepoint per protocol (i.e., missed doses are NOT made up). However, if the treatment is delayed past the next scheduled timepoint per protocol, the next scheduled timepoint will be delayed until dosing resumes.

If treatment is delayed  $> 6$  weeks, (from the missed dose) the subject must be permanently discontinued from study therapy, except as specified in discontinuation section below.

## 6.5. Discontinuation Criteria

Treatment should be permanently discontinued for the following:

- Any Grade 2 drug-related uveitis or eye pain or blurred vision that does not respond to topical therapy and does not improve to Grade 1 severity within the re-treatment period OR requires systemic treatment

- Any Grade 3 non-skin, drug-related adverse event lasting > 7 days, with the following exceptions for drug-related laboratory abnormalities, uveitis, pneumonitis, bronchospasm, diarrhea, colitis, neurologic adverse event, hypersensitivity reactions, and infusion reactions
  - Grade 3 drug-related uveitis, pneumonitis, bronchospasm, neurologic adverse event, hypersensitivity reaction, or infusion reaction of any duration requires discontinuation
  - Grade 3 drug-related laboratory abnormalities do not require treatment discontinuation except those noted below
- Grade 3 drug-related thrombocytopenia > 7 days or associated with bleeding
- Any drug-related liver function test (LFT) abnormality that meets the following criteria require discontinuation:
  - AST or ALT > 5 x ULN (grade 3)
  - Total bilirubin > 3 x ULN (grade 3)
  - AST or ALT > 3 x ULN **and** total bilirubin > 2 x ULN
- Grade 3 adrenal insufficiency
- Any Grade 4 drug-related adverse event or laboratory abnormality, except for the following events which do not require discontinuation:
  - Isolated Grade 4 electrolyte imbalances/abnormalities that are not associated with clinical sequelae and are corrected with supplementation/appropriate management within 72 hours of their onset
  - Grade 4 neutropenia lasting 7 days or less
  - Grade 4 lymphopenia or leucopenia
  - Grade 4 drug-related endocrinopathy adverse events, such as ACTH deficiency, hyper- or hypothyroidism, or glucose intolerance, which resolve or are adequately controlled with physiologic hormone replacement (corticosteroids, thyroid hormones) or glucose-controlling agents, respectively, may not require discontinuation after discussion with and approval from the Principal Investigator. However, grade 3 adrenal insufficiency requires nivolumab discontinuation, as above.
- Any dosing interruption lasting > 6 weeks (from scheduled dose) with the following exceptions:
  - Dosing interruptions to allow for prolonged steroid tapers to manage drug-related adverse events are allowed. Prior to re-initiating treatment in a subject with a dosing interruption lasting > 6 weeks, the sponsor-investigator must be consulted. Tumor assessments should continue as per protocol even if dosing is interrupted
  - Dosing interruptions > 6 weeks that occur for non-drug-related reasons may be allowed if approved by the sponsor-investigator. Prior to re-initiating treatment in a subject with a dosing interruption lasting > 6 weeks, the Principal Investigator must be consulted. Tumor assessments should continue as per protocol even if dosing is interrupted.

- Requirement for 10 mg per day or greater prednisone or equivalent for more than 12 weeks
- Any adverse event, laboratory abnormality, or intercurrent illness which, in the judgment of the site investigator, presents a substantial clinical risk to the subject with continued nivolumab dosing

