## 16. APPENDICES

**Appendix 1: Management of immune-related Adverse Events**

**Appendix 2: Information sheet for shipment of preliminary PD-L1-positive cases**

**Appendix 3: Instructions for peripheral blood collection for exploratory studies**

## Appendix 1: Management of Immune-Related Adverse Events

Immune-related adverse reaction	Severity	Treatment modification
Immune-related pneumonitis	Grade 2 pneumonitis	Withhold dose(s) until symptoms resolve, radiographic abnormalities improve, and management with corticosteroids is complete
	Grade 3 or 4 pneumonitis	Permanently discontinue treatment
Immune-related colitis	Grade 2 diarrhoea or colitis	Withhold dose(s) until symptoms resolve and management with corticosteroids, if needed, is complete
	Grade 3 diarrhoea or colitis	Withhold dose(s) until symptoms resolve and management with corticosteroids is complete
	Grade 4 diarrhoea or colitis	Permanently discontinue treatment
Immune-related hepatitis	Grade 2 elevation in aspartate aminotransferase (AST), alanine aminotransferase (ALT), or total bilirubin	Withhold dose(s) until laboratory values return to baseline and management with corticosteroids, if needed, is complete
	Grade 3 or 4 elevation in AST, ALT, or total bilirubin	Permanently discontinue treatment
Immune-related nephritis and renal dysfunction	Grade 2 or 3 creatinine elevation	Withhold dose(s) until creatinine returns to baseline and management with corticosteroids is complete
Immune-related endocrinopathies	Grade 4 creatinine elevation	Permanently discontinue treatment
	Symptomatic Grade 2 or 3 hypothyroidism, hyperthyroidism, hypophysitis, Grade 2 adrenal insufficiency, Grade 3 diabetes	Withhold dose(s) until symptoms resolve and management with corticosteroids (if needed for symptoms of acute inflammation) is complete. Treatment should be continued in the presence of hormone replacement therapy a as long as no symptoms are present
	Grade 4 hypothyroidism, Grade 4 hyperthyroidism, Grade 4 hypophysitis, Grade 3 or 4 adrenal insufficiency, Grade 4 diabetes	Permanently discontinue treatment
	Grade 3 rash	Withhold dose(s) until symptoms resolve and management with corticosteroids is complete
	Grade 4 rash	Permanently discontinue treatment
Immune-related skin adverse reactions	Stevens-Johnson syndrome (SJS) or toxic epidermal necrolysis (TEN)	Permanently discontinue treatment
	Grade 3 (first occurrence)	Withhold dose(s)
	Grade 3 myocarditis	Permanently discontinue treatment

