## Hepatic Adverse Event Management Algorithm

Rule out non-inflammatory causes. If non-inflammatory cause, treat accordingly and continue I-O therapy. Consider imaging for obstruction.

[figure not shown]
Patients on IV steroids may be switched to an equivalent dose of oral corticosteroids (e.g. prednisone) at start of tapering or earlier, once sustained clinical improvement is observed. Lower bioavailability of oral corticosteroids should be taken into account when switching to the equivalent dose of oral corticosteroids.

\*I-O therapy may be delayed rather than discontinued if AST/ALT ≤ 8 x ULN and T.bili ≤ 5 x ULN.

\*\*The recommended starting dose for grade 4 hepatitis is 2 mg/kg/day methylprednisolone IV.

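### Section 6.5 and Appendix 1 contradict each other on stopping for some Grade 3 liver events and for controlled Grade 4 endocrine events, and the infusion volume cap is stated two ways

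*Combined protocol and SAP*

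**What the plan says.** Section 6.1 hands immune-related toxicity to the appendix: "Please see Appendix 1 for tables summarizing management of immune-related adverse events plus management algorithms for specific organ systems". It gives no express rule for cases where Section 6 and Appendix 1 differ.

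**Liver.** Section 6.5 requires permanent discontinuation for drug-related AST or ALT above 5 x ULN or total bilirubin above 3 x ULN, labelling both thresholds Grade 3. It also stops for AST/ALT above 3 x ULN combined with bilirubin above 2 x ULN. The Appendix 1 table lists "Grade 3 or 4 elevation in AST, ALT, or total bilirubin" and likewise says to discontinue permanently. The footnote to the hepatic algorithm in the same appendix says "I-O therapy may be delayed rather than discontinued if AST/ALT" is at most 8 x ULN and bilirubin at most 5 x ULN.

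**Endocrine.** Section 6.5 stops for Grade 4 drug-related events but carves out "Grade 4 drug-related endocrinopathy adverse events, such as ACTH deficiency, hyper- or hypothyroidism, or glucose intolerance, which resolve or are adequately controlled" by hormone replacement or glucose-controlling agents; these "may not require discontinuation after discussion with and approval from the Principal Investigator". The Appendix 1 row for "Grade 4 hypothyroidism, Grade 4 hyperthyroidism, Grade 4 hypophysitis, Grade 3 or 4 adrenal insufficiency, Grade 4 diabetes" says to discontinue permanently, with no such carve-out. At Grade 3, Section 6.5 stops non-skin events lasting more than 7 days, and its exceptions do not include endocrinopathy. Section 6.4 and the Appendix 1 row for lower-grade endocrine events let treatment resume once the event is controlled on hormone replacement.

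**Infusion volume.** Section 5.2 caps the infusion at 160 mL, with a 4 mL/kg limit for patients under 40 kg. Section 10.1.2 caps it at 120 mL and allows 1 to 10 mg/mL.

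**The concern.** The liver and endocrine rules decide whether nivolumab is restarted after serious toxicity. The patients have no metastases on conventional imaging (Section 3.1) and may be treated for up to 2 years (Section 6.7). Section 1.6 reports no objective responses to nivolumab in phase I trials in advanced castration-resistant disease, so tolerance for avoidable toxicity should be low.

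Patients are treated at more than one institution (Section 8.5, Appendix 3). Two sites could handle the same event differently, each pointing to printed text. A site that follows the hepatic footnote would breach Section 6.5, and a site that uses the Section 6.5 endocrine exception would breach the Appendix 1 table. Safety is a secondary endpoint (Section 2.2.2), and discontinuations are part of the safety summary in the synopsis, so uneven handling would also blur what is reported.

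**Working it through.** The plan gives no figure to reproduce on this point. The check sets the texts side by side and does the arithmetic for the volume caps.

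**1. Liver.** Section 6.5 itself equates Grade 3 with AST/ALT above 5 x ULN and bilirubin above 3 x ULN, so the table row can be read on the same scale. Illustrative values, in multiples of ULN:

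| AST/ALT | Bilirubin | Section 6.5 | Appendix 1 table | Within footnote's delay limits (8 x and 5 x) |
|---|---|---|---|---|
| 6 | 1 | stop | stop | yes |
| 2 | 4 | stop | stop | yes |
| 7 | 4 | stop | stop | yes |
| 8 | 5 | stop | stop | yes |
| 9 | 1 | stop | stop | no |
| 6 | 5.5 | stop | stop | no |

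The conflict therefore covers AST/ALT above 5 and up to 8 x ULN with bilirubin at most 5 x ULN, or bilirubin above 3 and up to 5 x ULN with AST/ALT at most 8 x ULN. Within it, Appendix 1 disagrees with itself as well as with Section 6.5. Values such as AST/ALT 4 x with bilirubin 2.5 x ULN meet the combined rule in Section 6.5, which the table does not print. That is a gap in the table and is not counted as a contradiction.

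**2. Endocrine.**

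| Event | Section 6 | Appendix 1 table |
|---|---|---|
| Grade 4 thyroid event or glucose intolerance/diabetes, controlled | may continue with Principal Investigator approval (6.5) | discontinue |
| Grade 3 thyroid, pituitary or diabetic event, more than 7 days, controlled | stop under 6.5 unless classed as a laboratory abnormality; may resume under 6.4 | withhold, then continue on replacement |
| Grade 3 adrenal insufficiency | stop (6.5) | discontinue |

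The first row is a direct contradiction. The second is secondary: Sections 6.4 and 6.5 pull apart, and the appendix sides with 6.4. Read literally, Section 6.5 could keep a controlled Grade 4 event on drug while stopping a controlled Grade 3 one. The third row is consistent.

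**3. Infusion volume.** Concentration = dose / volume, with the 480 mg dose of Section 5.2:

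- 480 / 48 = 10 mg/mL (undiluted)
- 480 / 120 = 4.0 mg/mL
- 480 / 160 = 3.0 mg/mL

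All lie within 1 to 10 mg/mL, so the concentration range does not settle which cap applies. Volumes of 48 to 120 mL satisfy both caps; only those above 120 and up to 160 mL are in dispute. The weight limit gives 4 x 40 = 160 mL at 40 kg, and 120 / 4 = 30 kg is the weight at which it equals 120 mL.

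**The case against.** The best defence is that Section 6 is evidently the operative text. Section 6.1 describes the appendix tables as summaries, and the visible gastrointestinal algorithm defers to the protocol. The hepatic figure is not shown, so its boxes may defer in the same way. The footnote is permissive, Section 6.5 is mandatory, and the table agrees with 6.5; a site that stops complies with every text. The Grade 4 endocrine exception needs Principal Investigator approval, which limits variation between sites.

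Much of this stands, and it limits the size of the point. It does not remove the contradictions: the footnote's printed limits overlap the Section 6.5 stop range, and the Grade 4 endocrine row has no exception.

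Three stronger readings are tempting but unsupported:

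- **That letting Section 6 govern would be unsafe.** A reader might infer this because Appendix 1 has stops for recurrent Grade 3 and persistent Grade 2 or 3 events. Section 6.5 has its own backstops: prednisone of 10 mg/day or more beyond 12 weeks, interruptions beyond 6 weeks (with exceptions), and any event the site investigator judges a substantial risk. The appendix row is also cut off in the available text.
- **That the Grade 3 endocrine item is a full conflict between Section 6 and Appendix 1.** It lies mainly between 6.4 and 6.5, and the laboratory-abnormality exception in 6.5 narrows it further.
- **That a general stricter-rule clause is the remedy.** It would reach algorithm content that is not shown. It would also need carve-outs, for example so that the gastrointestinal algorithm is not read as a new Grade 3 stop.

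**Conclusion.** The point holds for two toxicity rules and one preparation detail. The clearest contradiction is controlled Grade 4 endocrinopathy. The liver contradiction is confined to the range set out above and assumes that the hepatic footnote means what its printed limits say, since the box it belongs to cannot be seen. The Grade 3 endocrine wording is a secondary inconsistency. The volume mismatch is minor.

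These instructions should be reconciled because they bear on patient safety and on uniform handling across sites. A reader might infer that the trial's error rates are affected; they are not. The calculations in Section 12.1 rest on cohort sizes, assumed disease control rates and success thresholds, and none of these uses the stopping rules or the volume cap.

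**What to change.** Amend each item separately, without a blanket stricter-rule default.

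1. **Liver.** Delete the hepatic footnote, or align it to Section 6.5. If kept, it should permit delay only at AST/ALT up to 5 x ULN and bilirubin up to 3 x ULN, and not where the combined rule (above 3 x with above 2 x) is met.
2. **Endocrine, Grade 4.** If the Principal Investigator exception is intended, write it into the Grade 4 row of Appendix 1. If not, delete it from Section 6.5.
3. **Endocrine, Grade 3.** Add controlled endocrinopathy, other than adrenal insufficiency, to the exceptions in the Section 6.5 rule on Grade 3 events beyond 7 days, to match Section 6.4.
4. **Volume.** State one cap in Sections 5.2 and 10.1.2, confirmed by pharmacy. Use 120 mL until then, only because it satisfies both sections; no text shows that it is the intended figure. Keep the 4 mL/kg limit.

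The cost is one short amendment and a memo to sites. The downside is slightly less room to delay rather than stop after Grade 3 liver events. Visits, sample size, alpha and power are unchanged.

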## 6.6. Treatment of Nivolumab-Related Infusion Reactions

Since nivolumab contains only human immunoglobulin protein sequences, it is unlikely to be immunogenic and induce infusion or hypersensitivity reactions. However, if such a reaction were to occur, it might manifest with fever, chills, rigors, headache, rash, pruritis, arthralgias, hypo- or hypertension, bronchospasm, or other symptoms.

All Grade 3 or 4 infusion reactions should be reported as an SAE if criteria are met. Infusion reactions should be graded according to NCI CTCAE v5.0 guidelines.

Treatment recommendations are provided below and may be modified based on local treatment standards and guidelines as appropriate:

- Grade 1 symptoms: (Mild reaction; infusion interruption not indicated; intervention not indicated). Remain at bedside and monitor subject until recovery from symptoms. The following prophylactic premedications are recommended for future infusions:
  - Diphenhydramine 50 mg (or equivalent) and/or paracetamol 325 to 1000 mg (acetaminophen) at least 30 minutes before additional nivolumab administrations.
- Grade 2 symptoms: (Moderate reaction requires therapy or infusion interruption but responds promptly to symptomatic treatment [eg, antihistamines, non-steroidal anti-inflammatory drugs, narcotics, corticosteroids, bronchodilators, IV fluids]; prophylactic medications indicated for 24 hours). Stop the nivolumab infusion, begin an IV infusion of normal saline, and treat the subject with diphenhydramine 50 mg IV (or equivalent) and/or paracetamol 325 to 1000 mg (acetaminophen); remain at bedside and monitor subject until resolution of symptoms. Corticosteroid or bronchodilator therapy may also be administered as appropriate. If the infusion is interrupted, then restart the infusion at 50% of the original infusion rate when symptoms resolve; if no further complications ensue after 30 minutes, the rate may be increased to 100% of the original infusion rate. Monitor subject closely. If symptoms recur, then no further nivolumab will be administered at that visit. Administer diphenhydramine 50 mg IV, and remain at bedside and monitor the subject until resolution of symptoms. The amount of study drug infused must be recorded on the electronic case report form (eCRF). The following prophylactic pre-medications are recommended for future infusions:
  - Diphenhydramine 50 mg (or equivalent) and/or paracetamol 325 to 1000 mg (acetaminophen) should be administered at least 30 minutes before additional nivolumab administrations. If necessary, corticosteroids (recommended dose: up to 25 mg of IV hydrocortisone or equivalent) may be used.
- Grade 3 or Grade 4 symptoms: (Severe reaction, Grade 3: prolonged [ie, not rapidly responsive to symptomatic medication and/or brief interruption of infusion]; recurrence of symptoms following initial improvement; hospitalization indicated for other clinical

sequelae [eg, renal impairment, pulmonary infiltrates]). Grade 4: (life threatening; pressor or ventilatory support indicated). Immediately discontinue infusion of nivolumab. Begin an IV infusion of normal saline, and treat the subject as follows. Recommend bronchodilators, epinephrine 0.2 to 1 mg of a 1:1,000 solution for subcutaneous administration or 0.1 to 0.25 mg of a 1:10,000 solution injected slowly for IV administration, and/or diphenhydramine 50 mg IV with methylprednisolone 100 mg IV (or equivalent), as needed. Subject should be monitored until the investigator is comfortable that the symptoms will not recur. ***Nivolumab will be permanently discontinued.*** Site investigators should follow their institutional guidelines for the treatment of anaphylaxis. Remain at bedside and monitor subject until recovery from symptoms. In the case of late-occurring hypersensitivity symptoms (eg, appearance of a localized or generalized pruritis within 1 week after treatment), symptomatic treatment may be given (eg, oral antihistamine, or corticosteroids).

